6.3.19 Hospital admission: The ED provider determines if admission is necessary for the standard care pathway. The research team will request that the ED provider admit eligible subjects randomized to VRT whose VOG diagnosis is ‘central’ at the ED Index Visit. Those whose VOG diagnosis is ‘equivocal’ will have hospital admission determined by the ED provider in consultation with a neurologist, when available. Those whose VOG diagnosis is ‘peripheral’ will be discharged after safety MRI, unless the ED provider decides to admit ‘off protocol’ for safety.

6.3.20 Neuro-otology examination: All subjects will undergo a focused neuro-otology examination at the 1-week visit to evaluate ongoing and new clinical symptoms since the ED Index Visit, to assess the likely diagnosis, and to provide any necessary referrals or communication with other providers.

6.3.21 Laboratory-based vestibular testing: All subjects will undergo formal vestibular testing at the 1-week visit. This standard clinical vestibular testing battery (~3 hours) will include the following:

1. Subjective visual vertical (SVV) testing

This test requires the patient to re-position a mechanical light bar so it is oriented upright. Depending on site-specific procedures, this may occur using the ‘bucket test’ (described above).

2. Video-oculography (VOG) saccade accuracy testing

This test requires the patient to look from side to side.

3. Video-oculography (VOG) head impulse testing (vHIT), 6 semicircular canal planes.

This test involves ~15 rapid head rotations in the plane of each semicircular canal.

4. Video-nystagmography (VNG) with caloric testing.

This test involves a series of maneuvers designed to elicit nystagmus. These include looking side to side, blocking visual fixation, passive head shaking, positional tests (Dix-Hallpike, supine roll), and bithermal caloric testing (warm and cold water instilled into the ear canal) while supine.

5. Vestibular-evoked myogenic potentials (VEMPs), cervical (c-VEMPs) and ocular (o-VEMPs).

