7. RISKS

This is a low-risk study whose properties generally do not exceed that typically encountered in routine clinical care (bedside exam using the standard of care in neuro-otology/vestibular neurology; MRI brain imaging using standard clinical protocols). Other than the risks of contrast MRI, there are no specific procedures, situations, or materials that pose serious hazards to patients or personnel. Additional small risks relate to misdiagnosis and risks from subsequent inappropriate testing or treatments. While we hypothesize that the intervention (VOG-guided care) will substantially reduce the risks of misdiagnosis, we are in equipoise regarding the possibility that it may not, on average, prove beneficial (or that individual patients could be harmed).

Risks to human subjects fall into seven broad categories that affect both arms of the trial:

- I. **Risks of disclosure of protected health information (PHI)** [*equal risk in both arms*] (very low)
- II. **Risks from delays in care due to VOG testing** [*equal risk in both arms*] (rare)
- III. **Risks of video-oculography (VOG) with head impulse testing (HIT)** [*equal risk in both arms*] (rare)
 - a. Discomfort (increased dizziness, nausea) (infrequent)
 - b. Symptomatic bradycardia (rare, single case report⁶²)
 - c. Minor soft tissue neck injury (rare, with no known cases of any significant injury)
 - d. Minor discomfort or loss of facial (eye brow or eyelash) hair upon adhesive eye patch removal
- IV. **Risks of MRI testing with contrast (both arms)** [*similar risk in both arms*] (rare)
 - a. Inadvertent imaging of patient with contraindication (rare with standard screening procedures⁶⁸)
 - b. Risks of flying metallic objects (rare with standard precautions^{69,70})
 - c. Risks of auditory injury (rare with standard precautions^{69,70})
 - d. Risks of difficulty with cardiac resuscitation (unstable cardiac patients will be excluded)
- V. **Risks of missed diagnoses or undertesting** [*hypothesis to be tested: potentially differential risk*]
 - a. Missed stroke (estimated ~30% in standard care arm; hypothesized ~1% in VOG-guided arm)
 - b. Missed treatable vestibular disorders (~50% standard care; hypothesized ~1% VOG)
- VI. **Risks of incorrect diagnoses or overtesting** [*hypothesis to be tested: potentially differential risk*]
 - a. Imaging or admission for stroke evaluation (~50% standard care; hypothesized ~15% VOG)

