Statistical Analysis Plan Secondary Outcomes 1.1-1.7: A generalized linear model with a log link will be used for comparing the true positive rates (TPRs) of VRT and SOC. Without additional covariates, the model based score test is equivalent to a Pearson Chi-square test for unpaired data. The regression model will assess the influence of demographic and key clinical variables as exploratory subgroups. Generalized estimating equation (GEE)¹⁶¹ method will be used to account for clustering effects by hospital site or provider.

Secondary outcomes 8-9: Discharge and admission proportions: the following proportions are considered:

8. Central Discharge Proportion (central subgroup only, VRT vs. SOC)

Total discharge proportion of central causes VRT vs. SOC. Central causes determined based on 30-day adjudicated final diagnosis.

9. Peripheral Admission Proportion (peripheral subgroup only, VRT vs. SOC)

Total admission proportion of peripheral causes VRT vs. SOC. Peripheral causes determined based on 30-day adjudicated final diagnosis.

Statistical Analysis Plan 1.b.2: A logistic regression will be used to estimate the odds of discharge in two arms among subjects with central causes determined based on 30-day adjudicated final diagnosis. Similarly, a logistic regression will be used to estimate the odds of admission in two arms among subjects with peripheral causes determined based on 30-day adjudicated final diagnosis.

9.2.2 Aim 2 (Trial Outcome): Measure the impact of VRT on initial diagnostic work-up costs

Hypothesis 2: The VRT pathway is cost saving relative to current ED practice in diagnostic assessments.

Primary outcome 2: Total dollar costs of VRT as compared to SOC for diagnostic tests and consultations obtained during the ED index visit and hospital admission (for those admitted at the index visit). The cost for

VRT arm does not include the costs of protocol safety MRIs or any tests not specified by the pathway but ordered for clinical purposes by ED providers. It does include tests ordered as part of the VRT pathway by consultants or ED providers in the ‘equivocal’ pathway. Total costs will be calculated by multiplying fixed cost estimates (most recent year available average Medicare reimbursement in US dollars) by utilization rates for each ED index visit service tracked.

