9.3 Sample Size and Accrual

Powering Endpoint: AVERT will be powered to detect a clinically important difference in diagnosis accuracy of 90% vs. 75% (113 per arm). VRT diagnosis is anticipated to be nearly 100% accurate. We have shown that expert eye movement exams have 98.4% (n=187/190) accuracy for differentiating peripheral (vestibular neuritis) from central (stroke) vestibular disorders in acute, continuous vertigo.⁷³ We have now replicated these findings with the VOG device in 21 acute vertigo patients (100% accuracy). The gold standard

Table 3. Comparison of proportions power estimate (alpha 0.05, power 80%)

VOG Care Correct Diagnoses	Standard Care Correct Diagnoses	Per-arm sample (total study sample)
----------------------------------	---------------------------------------	---

for BPPV diagnosis is eye movement analysis,^{48,78} often by VOG,^{51,165} so we conservatively estimate that VOG accuracy across all vestibular conditions will be >90%. Diagnosis accuracy of routine ED care varies, estimated at <20% for BPPV and neuritis⁵ and ~70% for stroke, and lower (~50%) if stroke presents with isolated vertigo.^{7,135,136} Best

estimates suggest an overall correct ED diagnosis rate of about 56% for vestibular patients.¹¹⁴ In EDs with greater access to specialty consultations or frequent MRI neuroimaging, the proportion of correct diagnoses may range higher. We have powered the AVERT Trial for an anticipated worst case scenario of 90% VRT accuracy and 75% standard care accuracy (Table 3).

Recruitment Capacity: Our 3-site consortium has a total of ~180,000 ED visits per year. Chief symptoms of vertigo/dizziness account for ~3-4% of ED visits.^{15,123} Thus, our 3 sites have ~5,400-7,200 ED dizziness visits per year (~5-7 patients per 24hrs per site). Of these, we estimate ~20-30%²⁰ will meet inclusion criteria (~1-2 patients per 24hrs per site). We will screen during five designated 7-hr shifts weekly, performing VOG on ~3-5 patients per week, enrolling ~2-4 patients per month per site, taking ~3 years to reach 226.

Number of Strokes: With our inclusion criteria, we expect ~10-20% strokes (n=11-23 per arm). This will not yield firm conclusions about VOG stroke accuracy, but should be sufficient for Phase III trial planning.

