Total diagnosis accuracy optimized VRT vs. SOC using 30-day adjudicated final diagnoses categorized in one of six diagnosis categories (3 peripheral, 1 central, 1 medical/other, 1 non-diagnosis). We will use "Optimized VRT Diagnosis" and "ED SOC Diagnosis" compared to the "Adjudicated Final Diagnosis" based on ED index visit and 30-day follow-up clinical assessments. Optimized VRT diagnoses will be run using the final (end-of-trial) version of the VRT algorithm. Only SOC-arm subjects are used for this outcome, as VRT patient results will have been used to optimize the algorithm during the trial. VRT diagnoses in the SOC arm (algorithm not run during the trial), will be assigned based on the final, optimized algorithm; for this purpose, the ED SOC diagnosis will be assigned as the VRT diagnosis for algorithm results in the VRT-E group. This outcome measure reflects the estimated diagnostic accuracy of the end-of-trial automated algorithm.

5. Central-Peripheral Diagnosis Accuracy (all, VRT vs. SOC)

Total diagnosis accuracy VRT vs. SOC using 30-day adjudicated final diagnoses categorized as central (stroke, posterior fossa mass lesion, encephalitis, demyelinating disease, etc.) vs. non-central (includes peripheral vestibular, medical, psychiatric, non-diagnoses, etc.).

6. Central Discharge Proportion (central subgroup only, VRT vs. SOC)

Total discharge proportion of central causes VRT vs. SOC. Central causes determined based on 30-day adjudicated final diagnosis.

7. Peripheral Admission Proportion (peripheral subgroup only, VRT vs. SOC)

Total admission proportion of peripheral causes VRT vs. SOC. Peripheral causes determined based on 30-day adjudicated final diagnosis.

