2.3 Sample Size and Accrual

Powering Endpoint: AVERT will be powered to detect a clinically important difference in diagnosis accuracy of 90% vs. 75% (113 per arm). VRT diagnosis is anticipated to be nearly 100% accurate. We have shown that expert eye movement exams have 98.4% (n=187/190) accuracy for differentiating peripheral (vestibular neuritis) from central (stroke) vestibular disorders in acute, continuous vertigo.⁷³ We have now replicated these findings with the VOG device in 21 acute vertigo patients (100% accuracy). The gold standard for BPPV diagnosis is eye movement analysis,^{48,78} often by VOG,^{51,165} so we conservatively estimate that VOG accuracy across all vestibular conditions will be >90%. Diagnosis accuracy of routine ED care varies, estimated at <20% for BPPV and neuritis⁵ and ~70% for stroke, and lower (~50%) if stroke presents with isolated vertigo.^{7,135,136} Best estimates suggest an

Table 3. Comparison of proportions power estimate (alpha 0.05, power 80%)

VOG Care Correct Diagnoses	Standard Care Correct Diagnoses	Per-arm sample (total study sample)
99%	50%	15 (30)
95%	50%	19 (38)
90%	50%	25 (50)
99%	75%	38 (76)
95%	75%	59 (118)
90%	75%	113 (226)

overall correct ED diagnosis rate of about 56% for vestibular patients.¹¹⁴ In EDs with greater access to specialty consultations or frequent MRI neuroimaging, the proportion of correct diagnoses may range higher. We have powered the AVERT Trial for an anticipated worst-case scenario of 90% VOG accuracy and 75% standard care accuracy (Table 3).

Recruitment Capacity: Our 3-site consortium has a total of ~180,000 ED visits per year. Chief symptoms of vertigo/dizziness account for ~3-4% of ED visits.^{15,123} Thus, our 3 sites have ~5,400-7,200 ED dizziness visits per year (~5-7 patients per 24hrs per site). Of these, we estimate ~20-30%²⁰ will meet inclusion criteria (~1-2 patients per 24hrs per site). We will screen during five designated 7-hr shifts weekly, performing VOG on ~3-5 patients per week, enrolling ~2-4 patients per month per site, taking ~3 years to reach 226.

Number of Strokes: With our inclusion criteria, we expect ~10-20% strokes (n=11-23 per arm). This will not yield firm conclusions about VOG stroke accuracy, but should be sufficient for phase 3 trial planning.

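### Central Discharge Proportion is to be analysed only by ordinary logistic regression, which gives no finite log odds ratio if the VRT arm has no discharges; on the plan's own hypotheses that is likely, and no sparse-data method is named

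*Protocol*

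**What the plan says.** Protocol 9.2.1 lists Central Discharge Proportion as secondary outcome 8. Its method, under Statistical Analysis Plan 1.b.2, is: "A logistic regression will be used to estimate the odds of discharge in two arms among subjects with central causes". Central status comes from the 30-day adjudicated final diagnosis. No exact, penalised or other sparse-data method is mentioned.

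The SAP (section 2.2, exploratory outcome 6) keeps the outcome, as "Total discharge proportion of central causes VRT vs. SOC", but moves it to exploratory and states no model.

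Three other places bear on how many events to expect:

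- Protocol 9.3 and SAP 2.3 both state that "we expect ~10-20% strokes (n=11-23 per arm").
- Protocol section 7, item V.a: "Missed stroke (estimated ~30% in standard care arm; hypothesized ~1% in VOG-guided arm").
- Protocol 6.3.19: "The research team will request that the ED provider admit eligible subjects randomized to VRT whose VOG diagnosis is ‘central". Under 5.1.2, discharging such a patient against that request is recorded as a protocol deviation.

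**The concern.** The VRT pathway is designed to push discharges of central patients towards zero, and the central subgroup is small. A two-arm logistic regression has no finite log odds ratio when one arm has no events. Its standard error then depends on where the fitting routine stops, and the Wald interval and p-value carry no information. The closer VRT comes to its hypothesised performance, the more likely this is.

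Central Discharge Proportion is the outcome that counts patients with a central cause who were sent home. Without a stated alternative, the team would have to choose a rescue method after seeing a zero cell.

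**Working it through.** **1. The plan's own figures.** Protocol 9.3 powers the trial on a "difference in diagnosis accuracy of 90% vs. 75% (113 per arm"). The two-proportion formula with two-sided alpha 0.05, 80% power and a continuity correction returns 113. Expected strokes per arm are 0.10 × 113 = 11.3 and 0.20 × 113 = 22.6, which is the stated 11-23.

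**2. Inputs that are assumptions.** No discharge rate for central causes is given. I take 30% in standard care and 1% under VRT from the missed-stroke figures as proxies, and add VRT rates of 5% and 10% to allow for ED overrides and equivocal results. I take 11, 17 or 23 central patients per arm, which counts strokes only.

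**3. When the model breaks down.** With a of n discharged under VRT and b of n under standard care, the log odds ratio is ln[a(n−b) / b(n−a)] and its Wald standard error is √[1/a + 1/(n−a) + 1/b + 1/(n−b)]. Neither is finite if an arm has 0 or n events. For discharge rate r that has probability f(r) = (1−r)^n + r^n per arm, so

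P(no finite log odds ratio) = 1 − [1 − f(VRT)] × [1 − f(SOC)].

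Example, n = 11, VRT 1%: 0.99^11 = 0.895 and 0.70^11 = 0.020, so 1 − 0.105 × 0.980 = 0.897.

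| VRT rate | n = 11 | n = 17 | n = 23 |
|---|---|---|---|
| 1% | 90% | 84% | 79% |
| 5% | 58% | 42% | 31% |
| 10% | 33% | 17% | 9% |

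The problem lies almost wholly in the VRT arm: at 30%, standard care has no events in only 2.0% (n = 11) to 0.03% (n = 23) of trials.

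**4. Sensitivity.**

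- A zero VRT cell is more likely than not only if the VRT rate is below 1 − 0.5^(1/n): 6.1% at n = 11, 3.0% at n = 23.
- The Protocol's 187/190 expert accuracy implies 3/190 = 1.6% error; used as the rate, P(zero VRT discharges) is 84% (n = 11) to 69% (n = 23).
- If 10-30% of central patients are equivocal and 10-30% of those go home (assumed), the VRT rate is 0.9 × 1% + 0.1 × 10% = 1.9% up to 0.7 × 1% + 0.3 × 30% = 9.7%. P(zero VRT discharges) then runs from 81% to 33% at n = 11 and from 64% to 10% at n = 23.
- With an assumed 35 central patients per arm and VRT 1%, 0.99^35 = 70% of trials have no finite log odds ratio.

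**5. Worked case, 0/23 against 7/23.**

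- Ordinary logistic fit: the coefficient drifts towards minus infinity. One routine stopped at a standard error near 16,600 (Wald p = 0.999); another reached about 1.7 million without converging.
- Risk difference: 7/23 − 0 = 0.304. The Wilson limits are 0.156 to 0.509 for 7/23 and 0 to 0.143 for 0/23. Newcombe lower limit: 0.304 − √[(0.304 − 0.156)² + 0.143²] = 0.098. Upper limit: 0.304 + (0.509 − 0.304) = 0.509. The interval is 10 to 51 points.
- Fisher p = 0.009; score (Pearson) p = 0.004.
- Exact conditional odds ratio 0, 95% interval 0 to 0.58.

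**6. Power at VRT 1%, SOC 30%, by exact enumeration.**

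| Test | n = 11 | n = 17 | n = 23 |
|---|---|---|---|
| Wald (non-finite counted as not significant) | 1% | 3% | 11% |
| Fisher exact | 19% | 55% | 79% |
| Score (Pearson) | 39% | 73% | 89% |

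**The case against.** Four objections have force.

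**The 1% is not a discharge rate.** It is a hypothesised rate of missed stroke diagnosis. Central causes also include mass lesions, encephalitis and demyelinating disease. A central patient can go home without a VRT miss, because the ED provider makes the final admission decision and equivocal cases are managed by the provider and consultant. This stands: a reader might infer that the VRT arm will usually have no events, but the documents support that only if the rate is below about 3-6%.

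**The odds ratio does exist.** A reader might infer that no estimate can be had. The maximum-likelihood odds ratio is 0, on the boundary, and exact, profile-likelihood or penalised methods give a finite upper limit; in the worked case the profile limit is about 0.24. This stands. The plan, however, names none of these methods.

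**The plan does not name a Wald test.** Where it names a test for its log-link models, it is the score test. The very low power and the p-value near 1 therefore belong to default Wald output and are not something the plan prescribes. This stands too.

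**Little depends on it.** The outcome is exploratory in the SAP, Protocol 9.3 already disclaims firm conclusions about stroke accuracy, and the Phase III rule uses diagnostic accuracy and cost. Since the outcome is defined as a proportion, 0/23 against 7/23 would be visible whatever the regression printed. So it does not follow that the trial would lose its disposition result.

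One consideration runs the other way. If the completer restriction in Protocol 9.1 applies here, the subgroup shrinks and a zero cell becomes more likely.

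**Conclusion.** The point holds in a limited form. The only method stated in either document is one whose log odds ratio, Wald interval and Wald test break down when an arm has no discharges. The size of that risk depends on a discharge rate that the documents do not give: 79-90% of trials if the VRT rate is 1%, 31-58% at 5% and 9-33% at 10%, with standard care at 30% and 11-23 central patients per arm. More central patients would lower it, but at VRT 1% it is still about 70% with 35 per arm.

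What would be lost is a usable interval and test from routine output, together with a prespecified choice of method. The comparison itself remains estimable, and neither the primary outcome nor the Phase III decision is affected. This is a cheap improvement to a lower-tier outcome.

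**What to change.** In Protocol Statistical Analysis Plan 1.b.2 (the central-discharge part) and in SAP exploratory outcome 6, put the same text:

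> The discharge proportion in each arm will be reported with the risk difference and its 95% Newcombe (score-type) interval, with a score (Pearson) or exact test as the supporting test. Any odds ratio will come from Firth-penalised or exact logistic regression with a profile or exact interval.

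Name one supporting test before the data are seen, and align the outcome's status (secondary or exploratory) across the two documents.

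The cost is one sentence in each document and standard software; no new data are needed. The drawback is that Fisher's test is clearly conservative at about 11 per arm: power is 19% against 39% for the score test at VRT 1%, and 0/11 against 3/11 gives p = 0.21 against 0.06. The interval should therefore be the main result.

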9.3 Sample Size and Accrual

Powering Endpoint: AVERT will be powered to detect a clinically important difference in diagnosis accuracy of 90% vs. 75% (113 per arm). VRT diagnosis is anticipated to be nearly 100% accurate. We have shown that expert eye movement exams have 98.4% (n=187/190) accuracy for differentiating peripheral (vestibular neuritis) from central (stroke) vestibular disorders in acute, continuous vertigo.⁷³ We have now replicated these findings with the VOG device in 21 acute vertigo patients (100% accuracy). The gold standard

Table 3. Comparison of proportions power estimate (alpha 0.05, power 80%)

VOG Care Correct Diagnoses	Standard Care Correct Diagnoses	Per-arm sample (total study sample)
----------------------------------	---------------------------------------	---

for BPPV diagnosis is eye movement analysis,^{48,78} often by VOG,^{51,165} so we conservatively estimate that VOG accuracy across all vestibular conditions will be >90%. Diagnosis accuracy of routine ED care varies, estimated at <20% for BPPV and neuritis⁵ and ~70% for stroke, and lower (~50%) if stroke presents with isolated vertigo.^{7,135,136} Best

estimates suggest an overall correct ED diagnosis rate of about 56% for vestibular patients.¹¹⁴ In EDs with greater access to specialty consultations or frequent MRI neuroimaging, the proportion of correct diagnoses may range higher. We have powered the AVERT Trial for an anticipated worst case scenario of 90% VRT accuracy and 75% standard care accuracy (Table 3).

Recruitment Capacity: Our 3-site consortium has a total of ~180,000 ED visits per year. Chief symptoms of vertigo/dizziness account for ~3-4% of ED visits.^{15,123} Thus, our 3 sites have ~5,400-7,200 ED dizziness visits per year (~5-7 patients per 24hrs per site). Of these, we estimate ~20-30%²⁰ will meet inclusion criteria (~1-2 patients per 24hrs per site). We will screen during five designated 7-hr shifts weekly, performing VOG on ~3-5 patients per week, enrolling ~2-4 patients per month per site, taking ~3 years to reach 226.

Number of Strokes: With our inclusion criteria, we expect ~10-20% strokes (n=11-23 per arm). This will not yield firm conclusions about VOG stroke accuracy, but should be sufficient for Phase III trial planning.

Interim Analyses: We plan interim analyses to be conducted by the Johns Hopkins Biostatistics Center for review and evaluation by the DSMB (Human Subjects below). The primary concern is risk of misdiagnosis causing harm in the standard ED care arm, since safety MRIs in the VOG arm make harm from misdiagnosis unlikely. Our preliminary plan is to conduct statistical analyses on 30-day clinical events after 75 and 150 patients, but the interim analysis plan will be finalized in concert with the DSMB and institutional IRBs.

Decision Rule for Proceeding to Phase III: We will proceed to Phase III if Phase II suggests either the (1) total diagnosis accuracy point estimate for VRT (or expert VOG) is higher than that of ED standard care (Aim 1); or (2) total diagnosis accuracy is statistically equivalent (Aim 1), but costs are lower for VRT care (Aim 2). Based on scant available data, a Phase III trial using 30-day clinical events would likely need ~1,000-5,000 subjects. Such a trial could be accomplished at reasonable cost with 2-4 years of recruitment at ~10-25 ED sites.

